## LIST OF ABBREVIATION

AE	Adverse Event
AESI	AEs of special interest
ALT	Alanine Aminotransferase
ANC	Absolute Neutrophil Count
BID	Twice daily
BTK	Bruton Tyrosine Kinase
CLL	Chronic Lymphocytic Leukaemia
CMV	Cytomegalovirus
CNS	Central Nervous System
CR	Complete Remission
CT	Computed Tomography
CTCAE	Common Terminology Criteria for Adverse Event
ECG	Electrocardiography
ECOG	Eastern Cooperative Oncology Group
EORTC QLQC30	European Organization for the Research and Treatment of Cancer Quality of Life Questionnaire
Hb	Haemoglobin
HCV	Hepatitis C Virus
HIV	Human Immunodeficiency Virus
ICH	International Conference on Harmonisation
IGHV	Immunoglobulin Variable Heavy Chain
iwCLL	International Workshop on Chronic Lymphocytic Leukaemia
LDT	Lymphocyte Doubling Time
MCL	Mantle Cell Lymphoma
MedDRA	Medical Dictionary for Regulatory Activities
MRI	Magnetic Resonance Imaging
PI	Prescribing Information
PR	Partial Remission
PRL	Partial Response with Treatment-Induced Lymphocytosis
PRO	Patients-reported outcome
SAE	Serious Adverse Event
SLL	Small Lymphocytic Lymphoma
SoA	Schedule of Activities

Document Title:	Document ID:	BP04-01
Statistical Analysis Plan	Version Number:	3.1
	Effective Date:	25-Nov-2021

## 1. INTRODUCTION

The purpose of this document is to provide a description of the statistical methods and procedures to be implemented for the analysis of data from D8220C00022 study. This document is based on protocol version 1.0 Dated 01-SEP-2020. The statistical planning and conduct of analysis of the data from this study will follow the principles defined in relevant ICH-E9 guidelines. Any change from the planned analysis as described in the protocol, are detailed here, and any differences described here supersede the analysis as presented in the protocol.

## 2. Study Objective and Design

### 2.1 Study Objective

#### 2.1.1 Primary Objective

- To investigate the safety of Acalabrutinib among Patients with treatment naïve and R/R CLL/ SLL, and relapsed & refractory MCL in Indian Patient

#### 2.1.2 Secondary Objective

- To assess the efficacy of Acalabrutinib in Patients of CLL/SLL and relapsed & refractory MCL in Indian Patients.
- Patient-reported outcome (PRO)

### 2.2 Study Description

#### 2.2.1 Study Design

The study is a phase IV, open-label, single-arm, multi-centre, prospective study to be conducted in India. The study will evaluate the safety and efficacy of Acalabrutinib in Indian adult Patients with CLL/SLL and Patients with MCL who have received at least one prior therapy. The Investigator will be trained on the locally approved Prescribing Information (PI) before the enrolment of the first Patient at their site to ensure compliance and proper dosing of the study drug. Patients will be monitored throughout the study period for AEs /SAEs/AESI of Acalabrutinib.

Patients with CLL/SLL and MCL who are eligible to receive Acalabrutinib treatment as per locally approved PI and ratified by an independent clinical judgment of treating physician will be evaluated for inclusion into the current phase IV trial. To enrol approximately 100 Patients (90 Patients of TN & R/R CLL and 10 R/R MCL Patients) into the study, it is expected that approximately 150 Patients will need to be screened.

The study will be initiated after approval by the Ethics Committee. Patients will undergo the following phases: Screening/Enrolment Phase, Treatment Phase, and Follow-up Phase.

Document Title:	Document ID:	BP04-01
Statistical Analysis Plan	Version Number:	3.1
	Effective Date:	25-Nov-2021

The decision of Patients to participate in this study must not, in any way, impact the standard of care they are receiving or any benefits to which they are otherwise entitled. Prior to data collection, all Patients must sign an Informed Consent Form (ICF), allowing for data collection and source data verification to be performed in accordance with local requirements and Sponsor policy.

Two cohorts of Patients will be included in the current study (a) Patients with CLL/SLL who are treatment naïve or have received at least one prior therapy (N= 90) and (b) Patients with MCL who have received at least one prior therapy (N= 10). Potential Patients will undergo screening phase within 07 days prior to the first dose. Patients who meet the protocol-defined inclusion/exclusion criteria will be prospectively enrolled in the study. Acalabrutinib capsules 100 mg are administered twice daily (BID) for 06 cycles, starting from Cycle 1, Day 1, and continuing up to Cycle 6, Day 28; or until study drug discontinuation due to either disease progression or, unacceptable toxicity, or other reasons, whichever occurs earlier.

Acalabrutinib will be provided by the Sponsor to Patients in the Treatment Phase. The Sponsor shall also conduct laboratory investigations for safety and efficacy evaluations, including haematology, biochemistry, radiology, and electrocardiography (ECG), as mentioned in the SoA table.

### 2.2.2 Inclusion Criteria

1. Men and Women aged 18yrs or more.
2. Eastern Cooperative Oncology Group (ECOG) performance status of 0,1, or 2
3. Able to receive all outPatient treatments, all laboratory monitoring, and all radiologic evaluations.
4. The following laboratory parameters:
  - a. Absolute neutrophil count (ANC)  $\geq 750$  cells/ $\mu\text{L}$  or  $\geq 500$  cells/ $\mu\text{L}$  in Patients with documented bone marrow involvement, and independent of growth factor support 07 days before the assessment
  - b. Platelet count  $\geq 50,000$  cells/ $\mu\text{L}$  or  $\geq 30,000$  cells/ $\mu\text{L}$  in Patients with documented bone marrow involvement, and without transfusion support 07 days before the assessment
  - c. Aspartate transaminase (AST) and Alanine transaminase (ALT)  $\leq 2.0 \times \text{ULN}$
  - d. Total bilirubin  $\leq 1.5 \times \text{ULN}$
  - e. Estimated creatinine clearance of  $\geq 30$  mL/min
5. Refractory disease defined as achieving less than partial response with the most recent treatment within 6 months before study entry
6. Provision of signed, written and dated informed consent prior to any study-specific Procedures
7. The Patients of either CLL or MCL:
  - a. CLL Patients:

Document Title:	Document ID:	BP04-01
Statistical Analysis Plan	Version Number:	3.1
	Effective Date:	25-Nov-2021

i. Treatment naïve or  $\geq 1$  prior systemic therapy for CLL

ii. Diagnosis of CD20+ CLL that meets published diagnostic criteria (Hallek et al. 2018)

iii. An active disease that meets  $\geq 1$  of the following iwCLL 2018 criteria for requiring treatment:

- 1) Evidence of progressive marrow failure as manifested by the development of, or worsening of, anaemia and/or thrombocytopenia. Cut-off levels of Hb  $< 10$  g/dL or platelet counts  $< 100 \times 10^9/L$  are generally regarded as an indication for treatment. However, in some Patients, platelet counts  $< 100 \times 10^9/L$  may remain stable over a long period; this situation does not automatically require therapeutic intervention.
- 2) Massive (i.e.,  $\geq 6$  cm below the left costal margin) or progressive or symptomatic splenomegaly.
- 3) Massive nodes (i.e.,  $\geq 10$  cm in longest diameter) or progressive or symptomatic lymphadenopathy.
- 4) Progressive lymphocytosis with an increase of  $\geq 50\%$  over a 2-month period or Lymphocyte Doubling Time (LDT) in  $< 6$  months. LDT can be obtained by linear regression extrapolation of absolute lymphocyte counts obtained at intervals of 2 weeks over an observation period of 2 to 3 months; Patients with initial blood lymphocyte counts  $< 30 \times 10^9/L$  may require a longer observation period to determine the LDT. Factors contributing to lymphocytosis other than CLL (e.g., infections, steroid administration) should be excluded.
- 5) Autoimmune complications, including anaemia or thrombocytopenia poorly responsive to corticosteroids.
- 6) Symptomatic or functional extra-nodal involvement (e.g., skin, kidney, lung, spine).
- 7) Disease-related symptoms as defined by any of the following:
  - a) Unintentional weight loss of  $\geq 10\%$  within the previous 06 months.
  - b) Significant fatigue (i.e., ECOG performance scale 02 or worse; cannot work or unable to perform usual activities).
  - c) Fever  $\geq 100.5^\circ F$  or  $38.0^\circ C$  for 02 or more weeks without evidence of infection.
  - d) Night sweats for  $\geq 1$  month without evidence of infection.

**b. MCL Patients:**

i. Confirmed MCL with translocation t(11;14) (q13;q32) and/or overexpressed cyclin D1

ii. Measurable nodal disease (one or more lesions measuring  $\geq 2$  cm in the longest diameter)

iii. Relapsed after, or were refractory to, 1-5 previous treatments.

[figure not shown]
Document Title:	Document ID:	BP04-01
Statistical Analysis Plan	Version Number:	3.1
	Effective Date:	25-Nov-2021

### 2.2.3 Exclusion Criteria

1. Known polymphocytic leukaemia, Central Nervous System (CNS) lymphoma or leukaemia; or known history of (or currently suspected) Richter's syndrome
2. Treatment with chemotherapy, external beam radiation therapy, anticancer antibodies, or investigational drug within 30 days of the first dose of study drug
3. Prior radio-conjugated or toxin-conjugated antibody therapy
4. Anticoagulation therapy (e.g., warfarin or equivalent vitamin K antagonists) within 07 days of the first dose of study drug.
5. Major surgery  $\leq 30$  days before the first dose of study drug
6. History of stroke or intracranial haemorrhage  $\leq 6$  months before the first dose of study drug.
7. History of bleeding diathesis
8. Prior exposure to a B-cell lymphoma-2 (Bcl-2) inhibitor or B-cell receptor inhibitor like BTKs
9. Active Cytomegalovirus (CMV) infection or serologic status reflecting active Hepatitis B or C infection or known history of infection with Human Immunodeficiency Virus (HIV), or any uncontrolled active systemic infection.
10. Significant cardiovascular disease such as uncontrolled or symptomatic arrhythmias, Congestive Heart Failure, or Myocardial Infarction within 06 months of screening, or any Class 3 or 4 cardiac diseases as defined by the New York Heart Association Functional Classification, or QTcB  $> 480$  msec at screening.
11. Requiring treatment with proton-pump inhibitors (e.g., Omeprazole, Esomeprazole, Lansoprazole, Dexlansoprazole, Rabeprazole, or Pantoprazole).
12. Breastfeeding or pregnant.
13. Current life-threatening illness, medical condition, or organ/system dysfunction which, in the Investigator's opinion, could have compromised the Patient's safety or put the study at risk.
14. Concurrent participation in another therapeutic clinical trial.

Document Title:	Document ID:	BP04-01
Statistical Analysis Plan	Version Number:	3.1
	Effective Date:	25-Nov-2021

2.2.4 Study Flow Chart

Document Title:	Document ID:	BP04-01
Statistical Analysis Plan	Version Number:	3.1
	Effective Date:	25-Nov-2021

## 2.2.5 Study Plan

Study Phase	Screening Phase	Treatment Phase *		Follow-up Phase
Cycle		Cycles 1-6	EOT	EOS
Visit No.	1	2-7 (Day 1 of each cycle)	8	
Study Days	-6 to 0	1-168 (28 days per cycle)	170	28 days post-EOT
Screening/Enrolment visit				
Informed consent §	X			
Eligibility Criteria	X			
Demographics/ Review medical history	X			
ECOG Performance Status	X	X	X	
General Physical examination b	X	Symptom-directed physical examination only		
Concomitant medication recording	Continuous from the time of ICF until 28 days after the last Acalabrutinib dose in the treatment phase.			
Study Drug Administration				
Acalabrutinib dosing		The recommended dose is Acalabrutinib 100 mg capsules BID, starting on Day 1 Cycle 1, until disease progression or unacceptable toxicity. Each cycle of treatment is 28 days.		
Disease Evaluations (Disease characteristics will be performed as per routine clinical practice)				
Baseline Disease Characteristics	X			
Safety Evaluations (baseline and each treatment visit) *				
Physical examination b	X	Symptom-directed physical examination only		
Vital parameters c	X	X	X	
Adverse event monitoring	Continuous from the time of ICF until 28 days after last study dose of Acalabrutinib.			

Document Title:	Document ID:	BP04-01
Statistical Analysis Plan	Version Number:	3.1
	Effective Date:	25-Nov-2021

Study Phase	Screening Phase	Treatment Phase a		Follow-up Phase
		Cycles 1-6	EOT	
Cycle				
Visit No.	1	2-7 (Day 1 of each cycle)	8	
Study Days	-6 to 0	1-168 (28 days per cycle)	170	28 days post-EOT
12-lead ECG	X	X	X	
Lymph node biopsy d	X			
Next-generation sequencing (NGS)-CLL panel e	X			
Haematology f & Biochemistry g	X	X	X	
Urinalysis h	X	X	X	
Pregnancy Test i	X	X	X	
Chest X-ray j	X	X	X	
Efficacy Evaluations (once in 3 months)				
CT/MRI k	X	X	X	
EORTC QLQ-C30 Questionnaire	X	X	X	

§ Patients must sign the informed consent form before any study-specific procedures are performed.

\* Procedures conducted as part of the Patient's routine clinical management (e.g., blood count) and obtained before signing of the Informed Consent Form (ICF) may be utilised for screening or baseline purposes provided the procedures meet the protocol-specified criteria and were performed within the time frame (-6 to 0 day)

- Treatment phase from Day 1 to Day 168. The treatment with Acalabrutinib will be continued until disease progression or unacceptable drug-related toxicity, whichever occurs earlier.
- The screening physical examination will include, at a minimum, the general appearance of the Patient, height (screening only) and weight, and examination of the skin, eyes, ears, nose, throat, lungs, heart, abdomen, extremities, musculoskeletal system, lymphatic system, and nervous system. Symptom-directed physical examination, including tumour assessments by palpation, are done thereafter.
- Vital signs (blood pressure, heart rate, and temperature) will be assessed after the Patient has rested in the sitting position.

Document Title:	Document ID:	BP04-01
Statistical Analysis Plan	Version Number:	3.1
	Effective Date:	25-Nov-2021

- d. Lymph node biopsy will be conducted in Patients with lymphadenopathy. However, a report of previous lymph node biopsy performed within 06 months before the study enrolment could be considered if the Patient did not receive any medication during that period

Study Phase	Screening Phase	Treatment Phase a		Follow-up Phase
Cycle		Cycles 1-6	EOT	EOS
Visit No.	1	2-7 (Day 1 of each cycle)	8	
Study Days	-6 to 0	1-168 (28 days per cycle)	170	28 days post-EOT

- e. Next-generation sequencing will be conducted to understand the genetic profile in Indian settings. Molecular cytogenetics (FISH) for del(13q), del(11q), del(17p), trisomy 12 in peripheral blood lymphocytes; TP53 mutation; immunoglobulin variable heavy chain (IGHV) mutational status will be assessed before the start of treatment in CLL/SLL-naïve Patients, or CLL/SLL Patients who did not have their report. However, MCL Patients are Relapsed/Refractory and their previous report data will be used. A six months old report can be considered for both the conditions.
- f. Haematology will include a complete blood cell count [white blood cell count, haemoglobin (Hb), haematocrit, reticulocyte, and platelet count] and differential leukocyte count, including both percent and an absolute number of lymphocytes. Haematology need not be repeated on Cycle 1 Day 1 if screening haematology was within 5 days.

## 2.3 Randomization

Not Applicable

## 2.4 Blinding and Un-Blinding

Not Applicable

## 2.5 Interim Analysis

Interim analyses is planned for first 50 subjects who completes the study. All the primary safety analysis will be produced for the interim analysis.

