7. DISCONTINUATION OF STUDY DRUG

7.1 Discontinuation of study treatment

Patients may be discontinued from the investigational product in the following situations:

- Patient decision. The patient is at any time free to discontinue treatment without prejudice to further treatment.
- Adverse Event that in the opinion of the Investigator or the Sponsor contraindicates further dosing
- Severe non-compliance to study protocol that, in the opinion of the Investigator or Sponsor, warrants withdrawal, e.g., refusal to adhere to scheduled visits etc.
- Any AE that meets criteria for discontinuation, as defined in Appendix D
- Initiation of alternative anticancer therapy including another investigational agent
- Disease progression as per the Investigator's clinical and imaging assessment.
- Pregnancy or intent to become pregnant.

If the patient is discontinued from the study, the patient will be followed up until the start of subsequent anti-cancer intervention or up to a duration of 28 days, whichever is earlier.

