7.2 Withdrawal from the study

A patient may withdraw from the study (e.g., withdraw consent), at any time at his/her own request, without prejudice to further treatment.

A patient who considers withdrawing from the study must be informed by the Investigator that the day of withdrawal will be considered as the end of the study phase for the patient. However, the patient will still have the provision of spontaneous AE reporting.

If the patient withdraws consent for disclosure of future information, the Sponsor may retain and continue to use any data collected before such a withdrawal of consent.

If a patient withdraws from the study, he/she may request the destruction of any samples taken, and the Investigator must document this in the site study records.

A patient who withdraws consent will always be asked about the reason(s) and the presence of any adverse events (AE). The Investigator will follow up with patients, as medically indicated.

AstraZeneca or its delegate will request Investigators to collect information on patients' vital status (dead or alive; date of death when applicable) at the end of the study from publicly available sources, in accordance with local regulations. Knowledge of the vital status of all patients at the end of the study is crucial for the integrity of the study.

Refer SoA, Table 1, for data to be collected at the time of study discontinuation and follow-up and for any further evaluations that need to be completed.

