## 3. Population Analysis Set

### 3.1 Full Analysis Set

The Full Analysis Set (FAS) will consist of all enrolled Patients who received at least one dose of Acabrutinib.

Document Title:	Document ID:	BP04-01
Statistical Analysis Plan	Version Number:	3.1
	Effective Date:	25-Nov-2021

The FAS will be used for all analyses of safety and efficacy.

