##### 5.3 Disposition of Patients

Patient disposition table will be based on all enrolled Patients who consented to participate in the study. The following summaries will be included in the disposition table: total number of Patients screened in the study, number and percentage of Patients who failed screening, number and percentage of Patients who completed the study, and number and percentage of Patients who discontinued from the study with reason for discontinuation.

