## 8. Mock Tables

Table 14.1.1. Patient Disposition in the Study

	CLL/SLL (N=xx)	MCL (N=xx)	Total (N=xx)
	n (%)	n (%)	n (%)
Patients Screened	xx (xx.xx)	xx (xx.xx)	xx (xx.xx)
Screen Failures	xx (xx.xx)	xx (xx.xx)	xx (xx.xx)
Patients Completed the study	xx (xx.xx)	xx (xx.xx)	xx (xx.xx)
Patients Discontinued the study	xx (xx.xx)	xx (xx.xx)	xx (xx.xx)
Reason for Discontinuation			
Patient Decision	xx (xx.xx)	xx (xx.xx)	xx (xx.xx)
Adverse Event	xx (xx.xx)	xx (xx.xx)	xx (xx.xx)
Severe non-compliance to study protocol	xx (xx.xx)	xx (xx.xx)	xx (xx.xx)
Initiation of alternative anticancer therapy including another investigational agent	xx (xx.xx)	xx (xx.xx)	xx (xx.xx)
Disease progression	xx (xx.xx)	xx (xx.xx)	xx (xx.xx)
Pregnancy or intent to become pregnant	xx (xx.xx)	xx (xx.xx)	xx (xx.xx)
Other	xx (xx.xx)	xx (xx.xx)	xx (xx.xx)
Other 1	xx (xx.xx)	xx (xx.xx)	xx (xx.xx)
Other 2	xx (xx.xx)	xx (xx.xx)	xx (xx.xx)

- The Capital "N" in the column header represents the total number of all Enrolled Patients.
- The small "n" in summary statistics represents the total number of Patients.
- Percentages in the "Patients Screened", "Screen Failures", "Patient completed the study" and "Patients Discontinued the study" rows are based on the number of Patient in each group.
- Percentages in the "Reasons for Discontinuation" rows are based on the number of Patients Discontinued study in each group.
- Note: Screened Patients are those who signed the informed consent
- Source :Listing 16.2.1.1, listing 16.2.1.2

Document Title:	Document ID:	BP04-01
Statistical Analysis Plan	Version Number:	3.1
	Effective Date:	25-Nov-2021

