**Table 14.3.1. Summary of Adverse Event**

	CLL/SLL (N=xx) n (%)	MCL (N=xx) n (%)	Total (N=xx) n (%)
Patient Experience Any Adverse Event			
Yes	xx (xx.xx)	xx (xx.xx)	xx (xx.xx)
No	xx (xx.xx)	xx (xx.xx)	xx (xx.xx)
CTCAE grade			
Mild	xx (xx.xx)	xx (xx.xx)	xx (xx.xx)
Moderate	xx (xx.xx)	xx (xx.xx)	xx (xx.xx)
Severe	xx (xx.xx)	xx (xx.xx)	xx (xx.xx)
Life – Threatening or disabling	xx (xx.xx)	xx (xx.xx)	xx (xx.xx)
Death	xx (xx.xx)	xx (xx.xx)	xx (xx.xx)
Investigator’s causality rating against the Investigational Product			
Yes	xx (xx.xx)	xx (xx.xx)	xx (xx.xx)
No	xx (xx.xx)	xx (xx.xx)	xx (xx.xx)
Action Taken			
None	xx (xx.xx)	xx (xx.xx)	xx (xx.xx)
Non-drug treatment required	xx (xx.xx)	xx (xx.xx)	xx (xx.xx)
Hospitalization/ prolonged hospitalization	xx (xx.xx)	xx (xx.xx)	xx (xx.xx)
Diagnostic or clinical test(s) conducted	xx (xx.xx)	xx (xx.xx)	xx (xx.xx)
Drug Withdrawn	xx (xx.xx)	xx (xx.xx)	xx (xx.xx)
Patient Withdrawn			
Yes	xx (xx.xx)	xx (xx.xx)	xx (xx.xx)
No	xx (xx.xx)	xx (xx.xx)	xx (xx.xx)
Treatment taken			
Yes	xx (xx.xx)	xx (xx.xx)	xx (xx.xx)
No	xx (xx.xx)	xx (xx.xx)	xx (xx.xx)
Outcome			
Recovered without sequelae	xx (xx.xx)	xx (xx.xx)	xx (xx.xx)
Recovered with sequelae	xx (xx.xx)	xx (xx.xx)	xx (xx.xx)
Not recovered/ Not resolved	xx (xx.xx)	xx (xx.xx)	xx (xx.xx)
Recovering/ resolving	xx (xx.xx)	xx (xx.xx)	xx (xx.xx)
Unknown	xx (xx.xx)	xx (xx.xx)	xx (xx.xx)
Fatal	xx (xx.xx)	xx (xx.xx)	xx (xx.xx)

- The Capital "N" in the column header represents the total number Full Analysis Set.
- The small "n" in summary statistics represents the total number of Patients.
- Percentages in the "Patient Experience Any Adverse Event" rows are based on number of patient in each group.
- Percentages in the "CTCAE grade, Investigator’s causality rating against the Investigational Product, Action Taken, Patient Withdrawn, Treatment taken and Outcome" rows are based on number of Patient Experience Any Adverse Event in each group.
- Source :Listing 16.2.11.1, Listing 16.2.11.2

Document Title:	Document ID:	BP04-01
Statistical Analysis Plan	Version Number:	3.1
	Effective Date:	25-Nov-2021

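### SAP 2.5 builds the interim safety analysis on the first 50 patients to complete the study, with no data cut-off, so on its natural reading the analysed set is selected on a post-baseline outcome

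*SAP*

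**What the plan says.** SAP 2.5 has two sentences. The first reads "Interim analyses is planned for first 50 subjects who completes the study"; the second says that all primary safety analyses will be produced for it. No analysis set, cut-off date or rule for incomplete follow-up is given. The protocol's statistics section plans no interim, so nothing there fills the gap.

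SAP 3.1 defines the FAS as all enrolled patients with at least one dose and states "The FAS will be used for all analyses of safety and efficacy". Protocol 9.3 says the same. Neither makes an exception for an interim. SAP 6.1.1 lists reasons for discontinuation within the primary endpoint.

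Two places bear on what completion means:

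- Protocol 4.4 counts a patient as having completed the study once the last scheduled visit or procedure in the schedule of activities is done. The last contact is the end-of-study (EOS) phone call, 28 days after the end-of-treatment (EOT) visit.
- SAP 5.3 reports "Patients who completed the study, and number and percentage of Patients who discontinued from the study with reason for discontinuation" as separate groups. The named reasons in Table 14.1.1, for example "Initiation of alternative anticancer therapy including another investigational agent", repeat the Protocol 7.1 list of reasons for stopping study drug.

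**The concern.** Whether a patient completes is known only after treatment and can depend on how the drug was tolerated. An interim restricted to completers therefore conditions a safety analysis on something close to one of its own outcomes. Patients who die, withdraw consent or are lost before EOS cannot enter the set under either meaning of completion. Patients who stop drug early enter or not according to which meaning the programmer applies, so two careful programmers could produce different interim tables from the same data. The tables at stake are all the primary safety outputs, including the adverse-event summary in Table 14.3.1.

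**Working it through.** **1. The plan's own figure at n = 50.** Protocol Table 8 gives 0.0% (0.00%, 7.11%) for no events in 50. The exact upper limit is 1 − 0.025^(1/50) = 0.0711, which agrees. All 43 cells of Table 8 reproduce to two decimals. The table is sound, but its intervals describe incidence in treated patients only if the 50 were not picked by outcome.

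**2. When a patient completes under Protocol 4.4.** A full course gives EOT on Day 170 and EOS on Day 170 + 28 = 198. Under Protocol 4.1.2 to 4.1.4 an early stopper has an EOT visit and then the same 28-day contact, so a patient who stops on day *s* completes at about *s* + 28. A stop on day 56, for illustration, gives 56 + 28 = 84, which is 198 − 84 = 114 days sooner than a full course. Early stoppers who take the call therefore reach the front of the queue.

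Some never take it. Protocol 4.1.4 ends follow-up at loss to follow-up or consent withdrawal. Protocol 7.1 says "the patient will be followed up until the start of subsequent anti-cancer intervention or up to a duration of 28 days, whichever is earlier". Protocol 7.2 says "the day of withdrawal will be considered as the end of the study phase for the patient".

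**3. Share of early stoppers among the first 50, Protocol 4.4 meaning.** The documents give no early-stop rate, stop-time pattern or EOS attendance, so all three are assumed. Simulation inputs:

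- 100 patients and a true early-stop rate of 10%.
- Uniform accrual. First patient in Q4 2020 and last in Q2 2021 (Protocol 1.2) allow about 91 to 272 days; 91, 180 and 270 were run.
- Stop day within 1 to 168: early-weighted (Beta(1,2)), uniform, or late-weighted (Beta(2,1)).
- A fraction *r* of early stoppers reach EOS 28 days after stopping; the rest never do. Full-course patients complete on day 198.
- 6,000 runs per cell.

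Each entry below is the range over the three stop-time patterns, to be compared with the true 10%.

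| Accrual | r = 1 | r = 0.8 | r = 0.6 | r = 0.5 |
|---|---|---|---|---|
| 91 days | 17.3–19.7% | 13.9–15.7% | 10.5–11.8% | 8.9–10.0% |
| 180 days | 15.3–18.8% | 12.4–15.1% | 9.5–11.4% | 8.0–9.5% |
| 270 days | 13.8–17.3% | 11.2–14.0% | 8.6–10.7% | 7.3–9.0% |

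The share equals the true 10% at an EOS attendance of about 51% to 71%, depending on accrual and stop pattern. Above that, early stoppers are over-represented; below it, under-represented.

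**4. SAP disposition split instead.** If a patient who stops drug for an adverse event or progression counts as discontinued and not completed, the "Drug Withdrawn" and "Patient Withdrawn" rows of interim Table 14.3.1 are close to empty by construction. For comparison, an unselected 50 dosed patients, with true rate *p* of withdrawal for adverse events (assumed), would give:

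| p | Expected count, 50p | Chance of none, (1 − p)^50 |
|---|---|---|
| 2% | 1 | 0.364 |
| 5% | 2.5 | 0.077 |
| 10% | 5 | 0.005 |

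A forced 0/50 carries the 7.11% upper limit from step 1, which would exclude a true rate of 10%.

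**5. Timing-trigger reading.** With accrual over 272 days, the 50th patient enters at about day 136, and a full course completes at about 136 + 198 = 334, after accrual has closed. In the simulations all 100 patients had been dosed by the 50th completion. On this reading the FAS at the interim is about the whole cohort, many with incomplete follow-up.

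**The case against.** The strongest reply is that the two sections can be read together: the 50th completion fixes when the interim is run, and SAP 3.1 fixes who is analysed. The footnote to Table 14.3.1, which defines N as the full analysis set, fits this. If that was the intention, there is no conflict with SAP 3.1. This stands as a possible reading, but SAP 2.5 does not state it, and an analysis planned for the first 50 such patients most naturally names the patients analysed. The precedence clause in SAP 1 does not help, since both statements are in the SAP.

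A reader might infer three stronger things, none of which the documents support:

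- *That completion is undefined.* SAP 2.5 gives no definition, but Protocol 4.4 does and the SAP is based on that protocol. The gap is that the SAP's disposition tables appear to use the term differently.
- *That interim withdrawals for adverse events will be near zero.* This follows only from the disposition split, which is an inference from a shared list of reasons. The protocol separates stopping drug (7.1) from leaving the study (7.2), and Table 14.3.1 has separate rows for the two. Under Protocol 4.4, a patient who stops for an adverse event and takes the EOS call is a completer.
- *That the interim will make the drug look safer.* Step 3 goes in both directions, and every input that decides it is assumed.

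The consequence is also limited. There is no hypothesis test, no stopping rule is tied to the interim, the final analysis uses the FAS, and serious adverse events are reported to the sponsor within 24 hours regardless.

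**Conclusion.** The point holds, with limited reach. On its natural reading, SAP 2.5 selects the interim safety set on a post-baseline outcome, gives no cut-off, and departs from the FAS rule in SAP 3.1 and Protocol 9.3. Whichever definition of completion is used, deaths, consent withdrawals and losses before EOS are left out.

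For early stoppers the effect depends on the definition. Under Protocol 4.4 they could be about 7% to 20% of the set against an assumed true 10%, for EOS attendance between 50% and 100%. Under the disposition split, those who stop for an adverse event or progression are excluded. These figures rest on assumed stop rates, stop times, attendance and uniform accrual. The direction of bias in overall adverse-event and serious-adverse-event rates cannot be determined from the documents. Only the descriptive interim is affected. It should be corrected before the interim is programmed, but it does not threaten the trial's final conclusions.

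**What to change.** Replace SAP 2.5 with wording to this effect:

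*The interim safety analysis includes the first 50 FAS patients by date of first dose, whether or not they complete the study. It is run when the last of these has reached EOS, discontinued and finished follow-up, or died. All their data to that cut-off are included.*

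State also that completion of the study in SAP 5.3 and Table 14.1.1 has the Protocol 4.4 meaning, so that stopping drug and leaving the study are not merged.

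Keeping the 50th completion as a trigger and analysing everyone dosed by then would also agree with SAP 3.1. By step 5, however, it turns a 50-patient interim into a snapshot of nearly the whole cohort with incomplete follow-up, so it is not the better choice.

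The cost is a few sentences of SAP text and a small shift in the interim date, whose size depends on accrual and drop-out. No extra patients or data are needed.
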